5.3 Informed Consent and Randomization

5.3.1 Telephone Screen, Consent, and Baseline Assessment:

Version 2.1, updated 3/17/2021, VA Puget Sound IRB Protocol Template-Version: 12/2015 Page | 17

For those potential participants who do not return an opt-out postcard within 2 weeks (or who return the opt/in card), a research coordinator may telephone to:

- Describe study and answer questions.
- Assess eligibility, including potential exclusions for safety. (Section 5.4)
- Obtain consent under a waiver of documentation of written informed consent.
- Administer baseline surveys; or participant may complete paper copies and return via postage-paid mail.
- Baseline assessment must occur no more than twelve weeks after the date of the index weight.

5.3.2 Medical Clearance:

For individuals who consent at the telephone screen and have fulfilled safety requirements, study staff will send a secure email to the patient's primary care provider to inform them of their patient's participation and to alert us if there is any reason that their patient should not participate. If the primary care provider does not respond after four days, we will send a second email. If no response to the second email, we will send a third email informing the PCP that we will enroll the individual in three business day unless they contact us otherwise. We will inform interested participants if their provider responded that this intervention is not appropriate.

5.3.3 Randomization:

DELITE staff will perform stratified randomization into the usual care or intervention group at a ratio of 1:1 within strata defined by age (<65 vs. \geq 65), BMI (three categories: \geq 30 and <35 vs. \geq 35.0 and <40 vs. \geq 40.0 and <45), and population density (Rural vs. Urban). Randomization must occur no more than twelve weeks after the date of the index weight. We will notify participants of their randomization group via mail. The mailing will include a weight scale, water bottle with a DELITE logo for all participant and the intervention materials (DVDs, binder containing introduction/instructions and the GLB curriculum, scale, CalorieKing Fat & Carbohydrate Counter, and paper tracking booklets) for intervention participants.

5.3.4 Continuation of Usual Care:

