5.5 Study Evaluations

Table 5 shows the study measures and data collection schedule. We will send self-administered questionnaires to participants via mail with the option to complete and return by postage-paid mail. If the participant does not return the questionnaires by mail within two weeks, we may send a reminder letter or a study coordinator may attempt to administer them by telephone. To improve retention and the likelihood that participants will complete the follow-up evaluations, we will send a letter reminding them of their participation in the study at around the 4th, 8th, 16th, and 20th month after randomization.

5.5.1 Baseline Variables and Co-variates:

We will collect baseline variables and co-variates from CDW to the extent possible, and supplement with participant self-report surveys, MFP logs, and/or paper trackers.

5.5.2 Outcomes:

• Weight:

- For all participants, we will extract all outpatient-based weight measurements from CDW starting with 12 months prior index date through 27 months of follow up. For participants without a CDW weight:
 - We may include a reminder with the outcomes surveys to visit their primary care clinic to be weighed if a clinic visit is safe and feasible.
 - During times when a clinic visit is not feasible (i.e., currently, during SARS-CoV-2 pandemic), we will include a self-weight form with the outcomes surveys for those without a CDW weight to weigh themselves at home. The self-weight survey and instructions for self-weighing will be in lieu of a reminder to visit their clinic to avoid encouraging participants seeking medical care unnecessarily, given public health guidance to avoid healthcare settings for anything other than urgent care requiring in-person contact. All participants without a 24-month CDW outcome will be asked to self-weigh using a letter asking the participant to weigh themselves using the scales provided by DELITE at baseline. The mailing will include instructions about how to make the measurement (e.g., light indoor clothing, no shoes or other heavy items), a form to record the weight, and a postage-paid return envelope. If we do not receive a mailed response from participants within 2-weeks, a study coordinator may call the participant and ask them to weigh themselves and report the weight over the telephone.

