- Other weight loss interventions: We will monitor through CDW data extraction for participation in MOVE! and by patient report for participation in programs outside VA, and we will control for such use in secondary analysis.
- Engagement of participants to the intervention will be assessed by: Through MFP and/or mailed survey:
 - Number of GLB sessions viewed, modality used (DVD vs. online), and use of handouts;
 - Number and topic of contacts with lifestyle coaches.
- Cost: We will conduct a budget impact analysis and determine implementation costs using VA Managerial Cost Account (MCA) System.

Table 5. Measures and timing of data collection.

Variable	Potential source of data	12 months prior	3 months Baseline	12 months	24 months
Program reach, baseline characteristics, and covariates					
Height	CDW		x		
Comorbidities	CDW/self-report	x	x	x	x
Medications	CDW	x	x	x	x
Healthcare utilization	CDW	x	x	x	x
Distance from primary care clinic	CDW		x		
Demographics	CDW; Self-report		x		
Weight loss programs	CDW/self-report			x	x
Self-monitoring	Self-report			x	x
Outcome assessments					
Primary					
Weight	CDW (primary care-based measurement through 15 mos)		x		x
SF-12	Self-report		x	x	x
Secondary					
Weight	CDW (all outpatient measurements* through 27 mos) or participant measured*	x	x	*x	x
Physical activity	Self-report		x	x	x
Dietary quality/self-efficacy	Self-report		x	x	x
Sleep disturbance / impairment	Self-report		x	x	x
Blood pressure	CDW	x	x	x	x
HbA1c	CDW	x	x	x	x
Other weight loss interventions	CDW/self-report	x	x	x	x
Engagement	Self-report			x	x
Percent accepting invitation	Invitation response		x		
Cost**	MCA				x
Reach	CDW/self-report/study tracking		x		
Adverse Event Surveillance					
Event form	CDW/Self-report			x	x

**other potential sources are Health Economics Resource Center (HERC), Non-VA Medical Care Files, VA/CMS Data for Research, and VHA Support Services Center (VSSC) via the following tools: Compensation & Pension Record Interchange (CAPRI), the Computerized Patient Record System (CPRS), VistAWeb, VINCI.

5.5.3 Participant Payment:

After the 24-month time point, we will compensate participants \$20 for completing the 12- or 24-month survey packets. We will pay participants an additional \$10 if they complete both packets, for a total possible of \$30.

Following payment submission, we may mail a letter notifying participants that participation is complete and payment has been submitted.

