We anticipate that any misclassification of outcome measurement will be non-differential with respect to randomization and effectively biasing our results toward the null. We will attempt to minimize misclassification by using approaches to decrease measurement error within the CDW data as well as by collecting patient-measured data when necessary. We will use data collected from primary care clinics preferentially. We will not collect weight data that was part of hospital admissions because of potential of changes in weight due to management. We will ask participants to use the scales provided only when not available in the CDW. If we find no evidence of informative missingness we will be able to rely on our use of well-specified mixed models to test effects of the intervention as these are known to lead to valid conclusions even when data are missing at random (MAR).^{87,93} If we detect informative missing data patterns, we will apply sensitivity analyses using pattern mixture models.⁸² Complete case analysis will only be performed as a sensitivity analysis, to provide useful inference if the data are mostly complete and the bias introduced by dropping the small proportion of incomplete cases is negligible.

5.6.6 Interim Analyses:

We plan no formal interim analysis of efficacy or futility. We will provide interim safety reports semi-annually to the Data Monitoring Committee (DMC).

5.7 *Withdrawal of Subjects*

We do not anticipate a need to withdraw a participant from the research entirely. If a participant becomes pregnant, we become aware of a serious physical or mental health issue, or the participant's primary care provider notifies us that the individual should not continue the intervention, the participant will cease participation in the intervention activities of the research; however we will continue to follow the individual through completion of the study via CDW and self-report.

If a participant chooses to withdraw him/herself from the research, we will confirm with the individual that we may continue to follow him/her in CDW. If the individual declines, we will respect his/her choice and not collect additional data from CDW; however we will use any data collected up to the date of withdrawal.

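### For weight, the plan's assurance that outcome error biases toward the null is unsupported, and the 24-month home weights have no analysis by source

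*Combined protocol and SAP*

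**What the plan says.** Section 5.6.5 makes a general statement about outcome error: "We anticipate that any misclassification of outcome measurement will be non-differential with respect to randomization and effectively biasing our results toward the null". It then lists ways to reduce such error, among them "as well as by collecting patient-measured data when necessary". Primary care weights are preferred, and home scales are used only where CDW has no weight.

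Section 5.5.2 describes the home weights. While clinic visits are not feasible, "All participants without a 24-month CDW outcome will be asked to self-weigh" on the scale the study supplied, and to return the value on a form. If no form arrives within two weeks, "a study coordinator may call the participant and ask them to weigh themselves and report the weight over the telephone". Table 5 gives the source of the secondary weight outcome as outpatient CDW measurements through 27 months "or participant measured".

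On knowledge of allocation, Section 5.3.3 says: "We will notify participants of their randomization group via mail". The blinding described in Section 6.3 concerns investigators and the staff who collect and analyse follow-up data.

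The primary weight in Section 5.5.2 is the primary care CDW weight nearest 12 months, within a window of 9 to 15 months. All other weights are secondary.

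**The concern.** The sentence in Section 5.6.5 tells readers that whatever error the weights carry, the estimated effect is conservative. Two separate things are needed for that: the error must be the same in both arms, and equal error must shrink a mean difference. The second is false for a continuous mean. The first is doubtful for a number that an unblinded participant reads off a scale and reports.

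The arms also differ in ways that could affect reporting. Section 5.3.5 gives the intervention arm a goal of 5-10% weight loss, instruction in self-monitoring that may include weight, and reminders for 12 months.

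Sustained weight loss through 24 months is a stated secondary aim (Section 3.3) and two-year weight heads the secondary outcomes in the Abstract. Section 5.6.3 says that the exploratory secondary analyses will be reported with 95% intervals and p-values. A reader could take a 24-month benefit as a lower bound when the design does not guarantee that.

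**Working it through.** **Inputs from the plan (Sections 5.1, 5.3.3, 5.6.1 and Table 6).** 500 participants, 1:1; 20% attrition at 12 months; weight SD 50 lb with baseline correlation 0.97 (base), or 57.7 lb and 0.95 (conservative); planned differences 7.7 and 6.7 lb; two-sided alpha 0.025; power 90%.

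**Step 1: reproduce the plan's figure.** Per arm, n = 2 × (z for alpha + z for power)² × SD² × (1 − r²) / difference², with (2.241 + 1.282)² = 12.41.
- Base: 2 × 12.41 × 147.75 / 59.29 = 61.9, so 62; 62 / 0.8 = 77.5, so 78. The plan states 78.
- Conservative: 2 × 12.41 × 324.6 / 44.89 = 179.5, so 180; 180 / 0.8 = 225. The plan states 225.

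The sample size is not in question. The check confirms that the SD and correlation are being used as the plan uses them.

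**Step 2: does equal error pull the difference toward zero?** If error with the same mean m is added in both arms, the difference in means is (μ1 + m) − (μ0 + m) = μ1 − μ0. A simulation with 200 per arm, SD 50, correlation 0.97, a true effect of −7.7 lb, a 2 lb shift in both arms and added noise (4,000 runs per setting) gave:

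| Noise SD (lb) | Mean estimate (lb) | SE (lb) |
|---|---|---|
| 0 | −7.70 | 1.23 |
| 5 | −7.71 | 1.29 |
| 10 | −7.69 | 1.56 |

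The estimate stays put and the precision falls.

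**Step 3: what if the error differs by arm?** Let f be the share of 24-month weights that are home weights and b the mean under-report, with subscript 1 for intervention and 0 for usual care. If the sources are combined, bias in favour of the intervention = f1 × b1 − f0 × b0. The documents give neither f nor b, so these are assumptions.
- Equal shares, unequal reporting: f × (b1 − b0). At 30% and 1 lb this is 0.3 lb; at 50% and 3 lb it is 1.5 lb.
- Equal reporting error of 2 lb, unequal shares: 50% against 30% gives 1.0 − 0.6 = 0.4 lb toward the intervention; 30% against 50% gives 0.4 lb the other way.

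**Step 4: scale.** With 250 × 0.8 = 200 analysed per arm, SE = SD × √(1 − r²) × √(2/200).
- Base: 12.155 × 0.1 = 1.22 lb.
- Conservative: 18.017 × 0.1 = 1.80 lb.

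Under a true null, a nominal 5% test rejects with probability P(|Z + bias/SE| > 1.96). A bias of 0.3 lb with SE 1.80 gives 5.3%; 1.5 lb with SE 1.22 gives 23%. These SEs borrow 12-month correlations and attrition. If the 24-month correlation were 0.90 with SD 50 (assumed), SE = 50 × √(1 − 0.81) × 0.1 = 2.18 lb and the 1.5 lb case gives about 11%.

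**Step 5: is there a safeguard?** Section 5.5.2 validated clinic weights against staff-measured weights, and Section 2.3.2 compares clinic with research weights; neither covers home weights. The pattern-mixture and complete-case analyses in Section 5.6.5 address missing values, not the source of observed ones. No section gives a source indicator, a clinic-only 24-month analysis or a count of home weights by arm.

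**The case against.** The plan already limits the problem. The primary weight excludes home weights, CDW weights take precedence, both arms were mailed a scale, and the weighing instructions do not differ by arm. Arm differences in response are partly a missing-data matter, for which the plan has methods. All of this stands. It reduces the number and crudeness of home weights but does not make their reporting error equal by arm.

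The tempting reading that the intervention arm was trained to report weight loss to the study goes beyond the text. Under Section 5.3.5.2 coach contact after the first call is optional, and coaching ends at month 12, a year before these weights. Knowledge of allocation is enough to leave the premise unsupported.

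A reader might also infer that pooling is prescribed. It is not. No 24-month weight model is written, and pooling is suggested by a single row of Table 5. That row carries single asterisks with no matching note in the text as read, so a qualifying note may have been lost.

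The general sentence is not wrong for every outcome. Section 5.6.3 also plans logistic models, and non-differential misclassification of a binary outcome does generally attenuate. The criticism is confined to weight.

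Finally, it is tempting to make clinic-only weights the main 24-month analysis. The documents do not settle that choice. If 30-50% of weights were home weights, 100-140 of 200 per arm would remain, and the SE would rise to 1.45-1.72 lb (base) or 2.15-2.55 lb (conservative). Home weighing was introduced because people were told to avoid non-urgent clinic visits, so those with a clinic weight may be a selected group. Possible reporting bias would be exchanged for possible selection bias.

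**Conclusion.** The concern holds for the secondary 24-month weight contrast. The toward-the-null assurance is wrong for a mean difference even when error is equal by arm, and equality is unsupported for home weights. Bias is possible in either direction, including in favour of the intervention.

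Its size cannot be derived from the documents. The 0.3-1.5 lb figure rests on an assumed 30-50% share and an assumed 1-3 lb reporting gap. The rejection rates of 5% to 23% rest additionally on borrowed 12-month inputs. They are illustrations, not estimates of this trial's error rate.

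A reader might infer that the trial's main weight result is compromised, or that the 24-month result is known to favour the intervention. Neither follows: the 12-month co-primary weight takes no home weights, and nothing in the documents fixes the direction. The point is minor in severity but changes what may be claimed for the 24-month result.

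**What to change.** In Section 5.6.5:
- For weight, delete the clause claiming bias toward the null, and state that self-reported weights may carry error that differs by arm.
- Commit to reporting the number and share of 24-month home weights by arm.
- Write down the 24-month weight analysis. Keep the combined-source analysis and prespecify a mixed model on clinic (CDW) weights only as a sensitivity analysis.
- Optionally, add a sensitivity analysis that shifts home weights by a stated amount, separately by arm, and shows the range over which the conclusion holds. Weight source arises after randomization, so any term for it belongs in sensitivity analysis.

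The cost is SAP wording and one extra model run, with no new data collection. The clinic-only interval will be wider and may reflect who attended clinic, so the two analyses should be read together.

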In comparison to usual care, both self-directed lifestyle intervention and intensive coach-led group intervention produced comparable clinically significant weight loss over 2 years among adults who were overweight or obese with prediabetes and/or metabolic syndrome (**Figure 2**). This finding has important implications because weight regain is common in weight loss interventions, whereas weight loss maintenance for at least 2 years is a strong predictor of continued maintenance success.^{51,52} The self-directed intervention also led to significantly lower waist circumference and fasting plasma glucose, compared with usual care.¹⁵ A post-hoc analysis of E-LITE data found that mean (SD) change in the SF-12 physical component scores improved by 1.6 (4.7) in the self-directed intervention versus a decline of 0.4 (6.5) in the usual care control group ($p = .01$) and an increase of 0.7 (8.5) in the coach-led intervention ($p = 0.51$). In addition, increasing physical component scores were significantly correlated with weight loss in both interventions (**Figure 3**). The difference in physical component score change between the self-directed intervention and usual care (2.0; 95% CI, -0.1 to 4.0) was 4% of baseline (baseline M [SD], 50.5 [7.5]); 3% was the minimally important difference used in the DPP.⁵³ The SF-12 mental health scores changed slightly in both intervention

[figure not shown]

Figure 2. Estimated mean \pm SE weight change over a 24-month period, in kilograms (left y-axis) and as percentages (right y-axis), in the intention-to-treat population.

[figure not shown]

Figure 3. Correlation between changes in weight and SF-12 physical composite score (PCS) from baseline to 15 months.

groups and did not differ significantly from usual care. These findings are consistent with the DPP and other behavioral weight-loss intervention studies.⁵³⁻⁵⁵ They further demonstrate the favorable outcomes of the E-LITE self-directed intervention. As the first RCT that successfully translated the DPP-GLB lifestyle intervention into primary care in the U.S., E-LITE was cited as key evidence in the 2014 USPSTF behavioral counseling recommendations for CVD prevention in primary care.⁵⁶

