5.6 Data Analysis

5.6.1 Power/Sample Size:

This study is powered on weight and SF-12 PCS outcomes, using ANCOVA for 12-month follow-up weight adjusted for baseline weight, and applying a t-test for the 12-month SF-12 ⁷⁷. See Table 6 for a summary. A two-sided type I error rate of $\alpha = 0.025$ was chosen based on a multiple comparisons Bonferroni adjustment. In order to ensure adequate power for this pragmatic trial, we are enrolling 500 Veterans.

We based expected outcomes in D-ELITE on clinically meaningful outcomes. Regarding weight loss, we based it on the weight lost in E-LITE's self-directed arm among male participants (since we anticipate the majority of our Veteran participants will be male): 11 ± 2 lbs ⁶². This is an amount of weight loss likely to be clinically meaningful ³. We expect weight loss in the control condition to be similar to that achieved in the standard MOVE! program: 3.3 pounds ⁷⁸. Thus, we expect to be able to detect a 7.7-pound absolute difference in 12-month mean weight between treatment arms, which requires 78 patients per treatment arm (156 patients in total), assuming a 12-month weight standard deviation of 50 lbs ⁷⁹, correlation of 0.97 between baseline and 12-month weight, 90% power, two-sided Type I error rate $\alpha = 0.025$, and 20% attrition at 12 months ⁶². This scenario has a Cohen's d effect size of 0.154 ⁸⁰. A more conservative set of assumptions with a 6.7-pound difference (25% reduction in Cohen's d effect size) and a weaker correlation of 0.95 between baseline and 12-month weight measures requires 225 patients per treatment arm (450 patients in total) with all other assumptions unchanged.

For SF-12 PCS at 12 months, we assume a Minimal Clinically Important Difference (MCID) of a 5.00-point absolute mean difference for the SF-12 PCS ⁸¹ between treatment arms, with a standard deviation of 8.88 points based on unpublished E-LITE data, which corresponds to a Cohen's d effect size of 0.563 ⁸⁰. Also assuming 90% power, two-sided Type I error rate $\alpha = 0.025$, and 20% attrition at 12 months, this would require 100 patients per treatment arm (200 patients in total). A more conservative scenario that assumes a 4.33-point absolute mean difference (25%-reduced effect size) requires 176 patients per treatment arm (352 patients in total) with all other assumptions unchanged.

Table 6. Sample size requirements for 12-month weight, SF-12 PCS.

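### Missing 12-month SF-12 PCS is handled without using 12-month CDW weight, which leaves an avoidable risk of bias in either direction; adding weight is a cheap improvement

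*Combined protocol and SAP*

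**What the plan says.** Section 5.6.3 gives one model form, fitted separately to weight and to SF-12 PCS. Its terms are time (baseline or 12 months), the arm-by-follow-up indicator, age group, BMI category, urban residence and a patient random intercept. No post-baseline weight enters the PCS model. The section also promises to examine dropout for informative missingness, but names neither variables nor a test.

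Section 5.6.5 continues: "If we find no evidence of informative missingness we will be able to rely on our use of well-specified mixed models". It relies on missing at random (MAR) under that model. If informative patterns are found, pattern-mixture models are added as sensitivity analyses.

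The two co-primary outcomes come from different sources. SF-12 comes from a mailed or telephone survey (5.5). For weight, section 5.5.2 says "For all participants, we will extract all outpatient-based weight measurements from CDW". Section 2.3.1 reports, from a post-hoc E-LITE analysis, that "increasing physical component scores were significantly correlated with weight loss in both interventions". The text gives no coefficient.

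**The concern.** MAR is always conditional on what the model contains. Here it requires that, among patients with the same baseline PCS, arm and strata, returning the survey is unrelated to 12-month PCS. None of those variables carries weight change. A patient who lost little weight and did not return the survey is therefore treated as if their PCS change were like that of similar responders in the same arm, even when their 12-month weight is on file.

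Suppose response depends on weight change, and does so differently in the two arms. The PCS contrast is then shifted, on an outcome that 5.6.3 allows to be claimed on its own at 0.025. Part of the information needed to correct the shift may already be in the trial database.

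**Working it through.** **1. The plan's own figure.** Inputs from 5.6.1: a "5.00-point absolute mean difference for the SF-12 PCS", a "standard deviation of 8.88 points based on unpublished E-LITE data", two-sided alpha 0.025, 90% power and 20% attrition. The normal approximation gives n per arm = 2 × (2.241 + 1.282)² × (8.88/5.00)² = 78.3. The exact t-test gives 79.6, so 80, and 80/0.8 = 100 per arm as stated. The conservative case (4.33 points, SD 10.25) gives 140.4/0.8 = 175.5, so 176 as stated. Nothing below changes the sample size.

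**2. Assumptions not in the documents.**
- Correlation of 0.6 between baseline and 12-month PCS (the E-LITE change SDs imply roughly 0.4 to 0.86).
- Within-arm correlation r of 0.2 to 0.4 between weight loss and the part of 12-month PCS not explained by baseline.
- Weight loss unrelated to baseline PCS.
- Logistic non-response, with an odds ratio (OR) of 2 or 3 per SD less weight loss.

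**3. Formula.** Bias = r × S × (m_I − m_C). S is the residual PCS SD: 8.88 × √(1 − 0.6²) = 7.10. For each arm, m is the mean weight loss of responders above the arm mean, in SD units. It is found by setting the logistic intercept to give the stated missing rate and averaging over responders. At 20% missing, m = 0.129 (OR 2) or 0.186 (OR 3). At 30% it is 0.190 (OR 2) or 0.270 (OR 3). At 15% and OR 2 it is 0.098. It is 0 when response is unrelated to weight.

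Example: 0.4 × 7.10 × 0.186 = 0.53.

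| Non-response pattern | Formula, r = 0.2 / 0.3 / 0.4 | Simulation, 250 per arm |
|---|---|---|
| 20% missing, intervention only, OR 2 | +0.18 / +0.27 / +0.37 | +0.19 / +0.27 / +0.38 |
| 20% missing, intervention only, OR 3 | +0.26 / +0.40 / +0.53 | +0.25 / +0.38 / +0.50 |
| 20% missing, both arms, OR 2 | 0 / 0 / 0 | +0.03 / −0.02 / −0.02 |
| 20% missing, control only, OR 2 | −0.18 / −0.27 / −0.37 | −0.19 / −0.26 / −0.34 |
| 30% v 15% missing, OR 2 in both arms | +0.13 / +0.20 / +0.26 | +0.11 / +0.22 / +0.27 |
| 30% (OR 3) v 15% (unrelated) | +0.38 / +0.58 / +0.77 | +0.38 / +0.57 / +0.76 |

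The simulations used 1,500 runs per scenario, with a true difference of 2.0 in the first four rows and none in the last two. They used baseline-adjusted ANCOVA on responders. The random-intercept mixed model gave +0.44 (Monte Carlo SE 0.06) against +0.41 for ANCOVA in the same scenario.

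**4. The ends of the range.** If r is read as the correlation with PCS change, S becomes 8.88 × √(2 × 0.4) = 7.94. The largest value is then 0.4 × 7.94 × 0.186 = +0.59, and control-only selection at OR 2 gives −0.4 × 7.94 × 0.129 = −0.41. The negative end is smaller only because control-only selection was taken to OR 2. At OR 3 the formula gives the mirror image.

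**5. Extreme bound at 20% missing.** If exactly the fifth of the intervention arm with least weight loss is missing, m = 0.280/0.8 = 0.35. With r = 0.2 and PCS correlation 0.7, bias = 0.35 × 0.2 × 8.88 × √(1 − 0.7²) = 0.44. With r = 0.4 and correlation 0.5, it is 0.35 × 0.4 × 8.88 × √(1 − 0.5²) = 1.08.

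**6. Error rate.** With 200 responders per arm, SE = 7.10 × √(2/200) = 0.71. A bias of 0.53 under no PCS effect gives rejection probability of about Φ(−2.241 + 0.53/0.71) = Φ(−1.49) = 0.07, against 0.025. Simulated values for intervention-only selection at 20% missing were 0.03 to 0.09, and up to 0.125 in the last row of the table.

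**7. With 12-month weight added.** In the intervention-only scenarios the simulated bias fell to within 0.04 of zero. With weight known for only 80%, it was 0.1 or less in absolute size.

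**The case against.** Several points on the other side stand.

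- **Direction.** A reader might infer that the bias favours the intervention. The documents do not support this: nothing in them says non-response will be tied to poor weight loss more strongly, or be more frequent, in that arm. Equal selection gives about 0, and control-only selection attenuates the effect.
- **Availability.** A reader might also infer that non-responders' weights are usually known. No such proportion is given. Section 5.6.1 assumes 20% attrition for weight too, and 5.5.2 sends the reminder to be weighed, or the self-weigh form, with the surveys. Both outcomes may therefore be missing in the same people.
- **Strength of the link.** The E-LITE correlation is post hoc, covers the intervention arms only and has no coefficient in the text. The coach-led arm had comparable weight loss but a PCS gain of only 0.7. Using the self-directed arm's change SD of 4.7 for S, intervention-only bias at 20% missing is 0.2 × 4.7 × 0.129 = 0.12 to 0.4 × 4.7 × 0.186 = 0.35.
- **Existing safeguards.** The plan has reminder letters, telephone administration, payment, a missingness evaluation and conditional pattern-mixture models. These reduce the exposure. But the evaluation is not said to look at weight, and the pattern-mixture step is only a sensitivity analysis.
- **Timing.** The abstract says the 12-month questionnaires are complete, so changing the primary method now needs care.

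These points limit the size and certainty of the problem. They do not give a reason to leave a measured correlate unused.

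**Conclusion.** The point holds as a conditional weakness. The planned PCS analysis is valid under MAR only given baseline PCS, arm and strata, and it omits a measured variable that the protocol itself links to PCS change.

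At 20% missing, the plausible bias is roughly −0.4 to +0.6 points, or about 0 if selection is equal. A shift of 0.2 to 0.6 is 4% to 12% of the 5.00-point MCID and 10% to 30% of the 2.0-point E-LITE difference. These sizes rest on the assumed correlations and response mechanisms, not on figures in the documents. Shifts near 1 point arise only at the extreme bound and should not be quoted as expected. The sample size is unaffected. Label: cheap improvement.

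**What to change.** In 5.6.5, state that missing 12-month PCS will be handled by multiple imputation within arm from baseline PCS, the strata and 12-month CDW weight change. A joint weight-PCS model with unstructured patient-level covariance is an alternative. The contrast estimated stays the one in 5.6.3. Make this the PCS missing-data method rather than a step that depends on detecting informative missingness.

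Record the change, and that it was made without sight of results, before any comparison by arm. If the primary method can no longer be changed, make this a pre-specified sensitivity analysis that is always run.

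In either case, report PCS response by arm and by observed weight change, and the proportion of survey non-responders with a 12-month weight.

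The cost is modest programming and documentation, with no new data. It does not help non-responders who also lack a 12-month weight.
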